10.5.1 PK modeling data set

Observations below the lower limit of quantification (LLOQ) will be censored by setting the CENS column for these observation records to 1 and setting the corresponding dependent variable (DV) column to the LLOQ (→ M3 method). Observation records with missing values and records with missing times will be ignored. Records flagged to be ignored will be removed from the dataset. Observations not analysed in the PK modelling (i.e., all parasite count records) will be removed. As a result, the PK modelling dataset only contains Pyronaridine tetraphosphate dosing records and Pyronaridine blood concentration records.

10.5.2 PD modeling data set

Observations below the LLOQ will be censored by setting the CENS column for these observation records to 1 and the corresponding DV value to the LLOQ, i.e., 10 p/mL (→ M3 method). Total counts of parasites for which counts of gametocytes exceeded 10% of total counts are flagged to be ignored (by setting the column IGNORE to "gametocytes"). Observation records with missing values and records with missing times will be ignored. Records flagged to be ignored will be removed from the dataset. Observations not analysed in the PD modelling analysis (i.e., concentration records) will be removed. As a result, the PD modelling dataset only contains Pyronaridine tetraphosphate dosing records, total parasite counts (i.e., triplicates).

The model baseline parasitemia value is added to the dataset as geometric mean of parasite counts at time of first Pyronaridine tetraphosphate dose.

The total parasite counts will be log-transformed for the PD modelling and estimated individual PK model parameters will be added to the dataset as regressors.

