4.3 JUSTIFICATION FOR DOSE

Pyronaridine will be administered as a single oral dose on Day 8, with different doses to be tested across and within cohorts in order to effectively characterise the PK/PD relationship. Each cohort will comprise up to three dose groups, with participants randomised to a dose group on the day of dosing. For each cohort, the SDRT will meet between Day 0 and Day 8, to decide on the dose/s to be administered. Dose selection will be decided based on number of participants inoculated with the malaria challenge agent, and when applicable available data from previous cohorts.

The highest dose of pyronaridine administered will be no more than 720 mg. This dose is equal to the maximum single daily dose of pyronaridine administered to adult patients ≥ 65 kg treated with Pyramax® (pyronaridine/artesunate combination) in accordance with manufacturer's product information for the treatment of acute uncomplicated malaria. Pyramax® is administered as a multiple dose treatment course (daily dosing with 720 mg pyronaridine/ 240 mg artesunate over three days for adults ≥ 65 kg), thus the total exposure to pyronaridine following administration of a single dose of 720 mg in the current study is expected to be lower than occurs during a course of Pyramax® treatment. A dose of 720 mg may be required to determine the maximum killing rate (E_{max}) of pyronaridine in the IBSM model.

The lowest dose of pyronaridine administered in this study will be no less than 180 mg. Modelling studies using clinical PK data and preclinical PD data (*in vitro* and murine studies) have indicated that a dose as low as 180 mg may be required for parasite regrowth to occur following initial parasite clearance. Parasite regrowth is required in this study to calculate all PK/PD parameters (primary endpoint).

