Additional blood samples may be collected to evaluate the presence of sexual parasite stages (gametocytes) and other parasite lifecycle stages using quantitative reverse-transcriptase polymerase chain reaction (qRT-PCR). The qRT-PCR assays may target parasite transcripts including but not limited to: the female gametocyte-specific transcript *pfs25*, the male gametocyte-specific transcript *PfMGET*, and the ring-stage transcript *pfSBP-1* as appropriate. The samples may be taken at time points indicated by malaria 18S qPCR, or at the Investigator's discretion. The parasite lifecycle stage qRT-PCR data may be used to facilitate the calculation of the PK/PD parameters of pyronaridine (the primary endpoint). Further, the results may guide the requirement for Primacin® administration to participants prior to the end of study.

Parasite viability in *ex vivo* culture

Ex vivo growth is an indirect measure of parasite viability. While 18S qPCR quantifies all parasites (including those non-viable or dead in circulation), only viable parasites are able to replicate in *ex vivo* culture. Modelling of parasite growth observed *ex vivo* enables the fraction of viable parasites present in blood samples to be determined. The results of parasite *ex vivo* growth analyses will be supportive to malaria 18S qPCR data in determining the kinetics of parasite clearance following pyronaridine dosing (secondary endpoint).

Short term *ex vivo* cultures will be established from blood collected pre-pyronaridine administration (Day 8), then at the following hours post-pyronaridine administration while confined in the clinical unit: 4, 8, 12, 16, 20, 24, 48, 72 and 96. An additional blood sample will be collected prior to the initiation of Riamet® treatment in the event that treatment is initiated prior to Day 47±2.

Microscopic examination for evidence of parasitaemia or gametocytaemia may also be conducted at the Investigator's discretion.

Refer to the Laboratory Manual for sample preparation procedures and sample volumes.

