3.5 Endpoints

3.5.1 Primary Endpoint(s)

- The PK/PD relationship between pyronaridine blood concentrations and blood stage asexual parasitaemia.

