10.5 Data Assembly

First a master dataset will be assembled formatted according to the MMV dataset standard. (cf., "MS_IQdataset_V4_20210219.docx"). Blood concentration will be in ug/mL, total parasite levels in counts/mL, and doses in mg. Gametocyte data is in copies/uL.

Parasite data after the first administration of rescue medication is flagged by setting the IGNORE column to "Rescued". The time in hours is relative to the (first) Pyronaridine tetraphosphate administration time.

A general analysis dataset is derived from the master dataset. Gametocyte data will be converted to parasite counts following the instructions in "Analyzing RNA data by [name] Nov2017.docx". Total counts of parasites were flagged to be ignored (by setting the column IGNORE to "gametocytes") if counts of gametocytes exceeded 10% of total counts.

The viable parasites counts will be derived by multiplication of the viable fraction values with the mean parasite count at treatment administration.

A general analysis dataset is derived from the master dataset. The general analysis dataset will contain the following observations: Pyronaridine blood concentrations, total counts of parasites, as well as counts of gametocytes and viable parasite counts. In addition, dosing records for *P. falciparum* inoculation, Pyronaridine tetraphosphate administration and rescue medication administration will be defined. It is advised to define additional columns DOSELEVEL and DOSEMULT to indicate the dose amount and number of doses a participant received as covariate columns.

NLME datasets for the PK and PD modeling will be derived from the general dataset.

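### Deleting every count with more than 10% gametocytes drops usable upper bounds on asexual parasitaemia around nadir and early regrowth; left-censor these records at the total instead

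*SAP*

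**What the plan says.** - **Endpoint.** SAP 3.5.1 gives the primary endpoint as "The PK/PD relationship between pyronaridine blood concentrations and blood stage asexual parasitaemia".
- **Rule.** SAP 10.5 introduces the 10% flag and SAP 10.5.2 applies it to the PD modelling dataset: "Total counts of parasites for which counts of gametocytes exceeded 10% of total counts are flagged to be ignored". It continues: "Records flagged to be ignored will be removed from the dataset".
- **Censoring already planned.** In the same section, counts below the quantification limit stay in the model by the M3 method, with CENS set to 1 and "the corresponding DV value to the LLOQ, i.e., 10 p/mL".
- **Gametocyte counts.** SAP 10.5 states: "Gametocyte data will be converted to parasite counts following the instructions" of a separate document. The raw gametocyte data are in copies/µL.
- **When gametocytes are measured.** Protocol 8.1.6 makes the outpatient lifecycle sample discretionary, prompted by suspicion of gametocytes when parasitaemia is low and stable. Protocol 8.2.2 allows these data to support the primary endpoint but does not say how.
- **Why these samples matter.** Protocol 4.3 says regrowth is needed to calculate all PK/PD parameters. SAP 10.7 ties the MIC to the time of minimum parasite count.
- **What is absent.** No reason is given for 10%, and no sensitivity analysis of the rule is planned. The optional threshold sensitivity analysis in SAP 11.1.2 concerns only the secondary PRR regression.

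**The concern.** Some handling of gametocytes is needed, because 18S qPCR counts all parasites and the endpoint is asexual. Deletion, however, makes inclusion of a record depend on the asexual count itself. Among gametocyte carriers, records in which asexual parasites are high are kept and records in which they are low are dropped.

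A participant who stays suppressed for a long time, which points to a low EC50, may then contribute little after clearance. A participant who regrows early still contributes the rise. When EC50 varies between participants, this tilts the population estimate upward. With at most 18 participants, each profile carries weight. The uncertainty also passes into the simulations in SAP 10.8, which sample population parameters from their uncertainty distribution.

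The dataset rules are also uneven. A count below 10 p/mL is kept because an upper bound is information. A count of 200 p/mL with 190 gametocytes is discarded, although it bounds asexual parasites at about 200.

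**Working it through.** **1. The rule in terms of asexual count.** G/(A+G) > 0.10 is equivalent to A < 9G. The SAP does not derive the 10%, so there is no figure to reproduce.

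**2. Error if the total were kept as if asexual.** This is log10[1/(1−f)] for gametocyte share f: 0.046 at 10%, 0.10 at 20%, 0.30 at 50% and 1.0 at 90%. Some handling is therefore justified at high shares.

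**3. How much of the rise is lost.** Growth rate: GR = ln[5000/(2800/V)]/192 h. The inoculum of 2,800, the 5,000 p/mL and Day 8 (192 h) come from SAP 3.1; blood volume V is assumed.
- V = 4 L: ln(5000/0.70)/192 = 0.046/h.
- V = 6 L: ln(5000/0.467)/192 = 0.048/h.

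Time from the cut-off to the 5,000 p/mL regrowth threshold is ln(5000/9G)/GR. With GR = 0.047/h:

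| G (per mL, assumed) | Deleted if A below | Hours of rise kept |
|---|---|---|
| 5 | 45 | 100 |
| 20 | 180 | 71 |
| 50 | 450 | 51 |
| 100 | 900 | 36 |
| 300 | 2,700 | 13 |
| 556 | 5,004 | 0 |

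Three outpatient samples a week are 168/3 = 56 h apart. At 50/mL roughly one sample on the rise survives; at 300/mL often none. These times assume full growth; net growth is slower near nadir.

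**4. What a deleted record contains.** It is mostly asexual only if G < A < 9G, a gametocyte share of 10% to 50%. At full growth that band is crossed in ln(9)/GR, about 46 to 48 h, less than one sampling interval. Below it, gametocytes dominate.

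**5. Simulation without between-participant variability.** SAP Emax model with M3 at 10 p/mL and protocol sampling days; 6 participants at 360/540/720 mg; 100 replicates; 9 scenarios. Assumed: Emax 0.12/h, GR 0.047/h, Hill 3, 14-day terminal half-life, three EC50 values, G of 5, 50 or 200/mL falling with a 10-day half-life, log-SD 0.5 for both assays, and gametocytes measured at every outpatient sample.

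| Handling | EC50 bias | SD of log EC50 |
|---|---|---|
| Delete (SAP) | −0.8% to +0.2% | 1.1% to 5.7% |
| Left-censor at total | −1.3% to +0.3% | 1.1% to 5.1% |
| Subtract gametocytes* | −0.9% to −48% | – |
| Keep total | −4% to −64% | – |

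*Censored at the total if gametocytes exceed 50%.

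With asexual counts seen directly, the SD was 1.0-1.3%. Of outpatient records, 61-96% were flagged, and 48-76% of those lay within three samples of nadir. Only 1-23% of flagged records were mostly asexual; the share reached 34-100% in a shallow-nadir scenario (nadir about 50 p/mL). For one participant at 540 mg without regrowth and G = 50/mL, the SD was 9.6% with deletion and 2.6% with censoring. At G = 200/mL in that case both were unstable.

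**6. Simulation with between-participant variability.** Step 5 cannot show the selection effect described in the concern, because every participant shares one EC50. With 18 participants and a log-SD of 0.4 on EC50 (both runs use assumed values), EC50 bias relative to fully observed asexual counts was:

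| G (per mL) | Delete |
|---|---|
| about 20 | none |
| 100 | +2% to +3% |
| 300 | +6% to +11% |

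Left-censoring at the total gave about 0 to −3%, with similar SD.

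**The case against.** The strongest reply is that excluding contaminated records by a pre-specified cut-off is defensible. Keeping totals is clearly worse, and with no variability in EC50 deletion costs 1% bias or less and little precision in the pooled fit. Growth parameters are estimated before treatment and entered as regressors (SAP 10.6.1), so later regrowth timing still carries information. This stands as a reason to exclude rather than keep totals. It does not answer the result with between-participant variability, which the SAP plans to estimate.

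The extent may also be overstated. Lifecycle samples are discretionary, so fewer records than simulated would be flagged. Protocol 6.5.1 and SAP 9 both class Primacin as rescue medication, and SAP 10.5 flags parasite data after the first rescue medication for removal. Where it is given, later records leave the model whatever the 10% rule says. Both limits stand.

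The remedy has flaws. The bound is a noisy qPCR reading, not a fixed limit. A share just under 10% stays an exact value while one just over becomes a bound. A record of 1,000 with 110 gametocytes becomes at most 1,000 rather than 890. All true; the measured price is the small downward bias in step 6.

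A reader might infer that the rule removes mostly asexual samples. The 10% cut-off permits this, but the documents give no gametocyte shares, and in most simulated scenarios flagged records were mainly gametocytes. A reader might also infer that asexual counts can be recovered by subtraction. The two counts come from different assays joined by a conversion document not included here, and subtraction was biased by up to −48%.

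**Conclusion.** The point holds in a limited form. The rule deletes records according to the asexual level being modelled, mainly around nadir and early regrowth, and discards a usable upper bound that the planned coding could hold. The size is conditional on assumed values: negligible at about 20 gametocytes/mL, roughly +2-3% on EC50 at 100/mL and +6-11% at 300/mL. For fixed Emax, GR and Hill, the SAP's MIC is proportional to EC50 and would shift by the same percentage.

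A stronger reading, that the primary EC50 and MIC would be seriously distorted, is not supported. The documents give no gametocyte levels, and nothing in them indicates levels near 556/mL, where every tested record below 5,000 p/mL would be deleted. This is a worthwhile, inexpensive improvement to the primary dataset and does not invalidate the analysis.

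**What to change.** In SAP 10.5 and 10.5.2:

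1. Where gametocytes exceed 10% of the total, keep the record as left-censored at the observed total (CENS=1, DV=total) under the planned M3 method. If the total is itself below 10 p/mL, leave the bound at the LLOQ.
2. Run the current deletion rule as a sensitivity analysis.
3. Do not use plain subtraction of converted gametocyte counts.
4. Report the number of flagged records by participant and dose.
5. Give the reason for 10%. State whether the flag applies to each replicate or to the time-point mean, and how totals without a matching qRT-PCR sample are treated.
6. Apply the same handling to the simulated data in the visual predictive checks (SAP 10.6.1.1).

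The cost is a data-assembly change and one extra model run. The statistical downside is a downward bias of about 0-3% in simulation, because the bound is a noisy measurement. Trial conduct and sampling do not change.

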9.4.3 ANALYSIS OF THE SECONDARY ENDPOINTS

This study has three secondary endpoints.

Safety parameters:

The safety and tolerability of pyronaridine will be assessed by clinical review of the following parameters:

- AEs (including SAEs and AESIs)
- Vital signs
- 12-lead ECG
- Haematology, Biochemistry, urinalysis
- Physical examination

The analysis of this endpoint is discussed in Section 9.4.4 below.

Parasite clearance kinetics:

The parasite clearance kinetics following dosing with of pyronaridine will be determined by calculating the parasite reduction ratio over a 48 hour period (PRR₄₈) and corresponding parasite clearance half-life (PCt_{1/2}); the incidence of parasite regrowth (n and % per dose group) will be recorded.

The PRR₄₈ will be estimated using the slope of the optimal fit of the log-linear relationship of the parasitaemia decay. The optimal fit will be derived using summarised replicate parasitaemia data, which have been cleaned by dealing with potential outliers, values below the limit of detection and non-detectable values (ND). The optimal fit of the log-linear parasitaemia-by-time relationship is determined by using left and right censoring to systematically remove the potential lag phase and tail phase of the parasitaemia decay. The decay rate, estimated by the slope coefficient from the log-linear decay regression, will be calculated for each participant. The overall dose-specific PRR₄₈ will be estimated with its 95% CI by calculating the weighted average slope estimate and corresponding standard error (SE) using an inverse-variance method. Only participants who have optimal regression models with appropriate fit contribute toward the dose-specific PRR₄₈. Details will be presented in the SAP.

The parasite clearance half-life (Pt ½) will be derived from the optimal decay rate. PCt_{1/2} is a transformation of PRR₄₈ into a per hour clearance rate. Details regarding the calculation of this parameter will be presented in the SAP.

PK parameters:

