10.6.3. PD modeling

PD model development will be done using gradient based algorithms in IQRTools SysFit. The selected model will then be estimated with SAEM in Monolix to allow for estimation of IIV. Other appropriate methods may be used if advisable. As a general concept the changes in living parasite P are modeled as the effect of a net exponential growth rate GR and a killing or clearance rate $Kill$ due to Pyronaridine. The initial parasitemia P_{base} at time t_0 will be derived from the mean parasitemia which was observed at treatment administration and a parameter $PLerr$ to allow for population and individual deviations. The equations are expressed in the log-scale such as:

$$\frac{dPL}{dt} = GR - Kill$$
$$PL(t_0) = PL_{base} + PL_{err}$$

where $PL = \ln(P)$ is the log-transformed parasite counts.

Three different models describing the relationship of Pyronaridine blood concentration on the killing rate will be tested:

(1) The " E_{max} -model" assumes a direct effect of concentrations on parasite killing/clearance, such as:

$$Kill = E_{max} \cdot \frac{C_c^{Hill}}{C_c^{Hill} + EC_{50}^{Hill}}$$

where C_c is the concentration in the central compartment, E_{max} is the maximum effect of the drug, EC_{50} is the concentration that results in 50% of the maximum effect and $Hill$ is the Hill coefficient.

(2) The "Turnover model" implements an indirect response model reflecting the idea that the kinetics of drug-receptor binding lead to a lagged concentration-effect relationship, such as:

$$Kill = E_{max} \cdot R$$
$$\frac{dR}{dt} = k_{in} \left(\frac{C_c^{Hill}}{C_c^{Hill} + EC_{50}^{Hill}} - R \right)$$

where k_{in} represents the binding rate of the drug to a "receptor", which results in a lag-time in the response. Furthermore, EC_{50} represents the concentration that results in a 50% occupancy of the receptor which leads to 50% of the maximum effect given enough time to reach it.

(3) The "Clearance model" assumes that the observed parasites are a mixture of living and dead parasites. The drug has a direct effect on the killing rate of the parasites, and then the parasites are cleared, but still observed. Therefore, the equations, in the normal scale, are:

$$\frac{dP_{Alive}}{dt} = P_{Alive} \cdot (GR - Kill)$$
$$\frac{dP_{Dead}}{dt} = P_{Alive} \cdot Kill - CLpara \cdot P_{Dead}$$
$$Kill = E_{max} \cdot \frac{C_c^{Hill}}{C_c^{Hill} + EC_{50}^{Hill}}$$
$$P_{obs} = P_{Alive} + P_{Dead}$$
$$P_{Dead}(t_0) = 0$$

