where $CLpara$ is the clearance rate of dead parasites, and P_{obs} is the count of measured parasite. If viable parasitemia is available then it is possible to differentiate between the killing rate and the clearance rate. Otherwise, both populations are measured indistinguishably, and E_{max} is fixed to the *in vitro* E_{max} value for this model.

During base model building, the Hill coefficient may not be identifiable. Then the best value for the Hill coefficient will be determined by estimating models with fixed Hill coefficients and selecting the best model based on the Bayesian information criterion (BIC). Considered Hill coefficients are 1, 2, 3, 5, 7, and 10. If covariate modeling is performed, the Hill coefficient is fixed in the value determined in the base model building.

IIV will be assumed on all parameters but the Hill coefficient. Parameters are assumed to be log-normally distributed besides the log-transformed deviation from the baseline parasitemia value $PLerr$ for which normal distribution will be assumed. The standard deviation of the IIV will be fixed to 0.2 for the SysFit approach. When parameters are estimated with Monolix, standard deviations of the IIV will be estimated.

Using the SysFit approach for PD modelling, parameter estimation will be started from 24 initial guesses. Identifiability of the best fit will be analysed using the profile likelihood method.

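### Viable-parasite counts are derived and needed by the Clearance model but missing from the PD modelling dataset; their scaling is undefined and, separately, the ex vivo endpoint has no planned analysis

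*SAP*

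**What the plan says.** **Use of viable counts in the model**

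- SAP 10.5 builds a general analysis dataset whose observations include "total counts of parasites, as well as counts of gametocytes and viable parasite counts".
- SAP 10.5.2 describes the PD modelling dataset derived from it: "the PD modelling dataset only contains Pyronaridine tetraphosphate dosing records, total parasite counts (i.e., triplicates"). The only example it gives of records to drop is concentrations: "Observations not analysed in the PD modelling analysis (i.e., concentration records) will be removed".
- SAP 10.6.3 states: "Three different models describing the relationship of Pyronaridine blood concentration on the killing rate will be tested". These are the Emax, Turnover and Clearance models. For the third: "If viable parasitemia is available then it is possible to differentiate between the killing rate and the clearance rate". Failing that, Emax in this model is set to an in vitro value, which is not given.
- SAP 10.7 takes the key efficacy parameters from simulated viable parasites if the Clearance model is final.

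**Scaling**

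- SAP 10.5: "The viable parasites counts will be derived by multiplication of the viable fraction values with the mean parasite count at treatment administration".
- Protocol 8.2.2 says that modelling ex vivo growth "enables the fraction of viable parasites present in blood samples to be determined".

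**The ex vivo endpoint**

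- Protocol section 3 lists four secondary objectives, the fourth with parasite growth in ex vivo culture as its endpoint. SAP 3.4.2 keeps that objective.
- Protocol 9.4.3: "This study has three secondary endpoints". They are safety, clearance kinetics and PK.
- SAP 3.5.2 and section 11 cover the same three. Appendix Table A has no viability listing, table or figure. SAP 13 reports no change.

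**The concern.** The 18S qPCR assay counts dead parasites still in circulation as well as living ones; protocol 8.2.2 says so and gives this as the reason for ex vivo culture. The Clearance model represents both populations, and viable counts are the data that tell them apart. If the modelling dataset is built as 10.5.2 describes, the model loses those data and takes its maximum killing rate from outside the trial. Emax is one of the three parameters that define the primary endpoint in protocol 9.4.2, and protocol 4.3 justifies the top dose partly by the need to determine it.

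Two further matters affect the same data. The rule for turning a viable fraction into a count is right or wrong according to a definition the SAP does not give. And a listed secondary endpoint, for which participants give a pre-dose sample, nine post-dose samples and one before any early rescue treatment, has no planned analysis.

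**Working it through.** The plan states no figure on this point to reproduce. The check is a reading of the sections side by side and a solution of the SAP's own equations.

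**1. Do total counts separate killing from clearance?**

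Inputs from SAP 10.6.3: dP_Alive/dt = P_Alive (GR − Kill); dP_Dead/dt = P_Alive × Kill − CLpara × P_Dead; P_obs = P_Alive + P_Dead; P_Dead(t0) = 0. SAP 10.6.1 estimates GR from pre-dose counts, so GR is treated as known. At saturating concentration Kill = Emax. Write k = Emax − GR. Then

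P_obs(t) = P0 × [ (CLpara + GR)/(CLpara − k) × exp(−k t) − (k + GR)/(CLpara − k) × exp(−CLpara t) ].

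Exchanging k and CLpara leaves this expression unchanged. So (Emax, CLpara) and (CLpara + GR, Emax − GR) give the same total-count curve.

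The SAP's formula for the maximum reduction (10.7) is log10 PRR48 = 48 × (Emax − GR)/ln 10. The documents give no values for these rates, so the following are assumptions: GR = 0.048/h, P0 = 5,000 per mL.

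| | Solution A | Solution B |
|---|---|---|
| Emax (per h) | 0.30 | 0.10 + 0.048 = 0.148 |
| CLpara (per h) | 0.10 | 0.30 − 0.048 = 0.252 |
| Total count at 24 h, share of P0 | 0.177 | 0.177 |
| Total count at 48 h, share of P0 | 0.016 | 0.016 |
| log10 PRR48 | 48 × 0.252/2.303 = 5.25 | 48 × 0.100/2.303 = 2.08 |
| Viable per mL at 24 h | 5,000 × exp(−0.252 × 24) ≈ 12 | 5,000 × exp(−0.100 × 24) ≈ 454 |

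The totals agree to rounding error at every ex vivo sampling time. The viable counts differ about 38-fold (454/12) at 24 h, so viability data would choose between the solutions. Over an assumed grid (GR 0.04, 0.048 and 0.07; Emax and CLpara of 0.30 and 0.10, 0.20 and 0.08, 0.20 and 0.25), the paired solutions differ by 1.0 to 3.3 in log10 PRR48. If Emax is fixed instead, each 0.01/h in the chosen value moves log10 PRR48 by 48 × 0.01/2.303 = 0.21.

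**2. Scaling of the viable fraction**

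Let f(t) be the fraction, T(t) the total count at the sample time and T(0) the count at dosing. The SAP computes f(t) × T(0).

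- If f(t) is a share of the current sample, the viable count is f(t) × T(t). The SAP's rule overstates it by T(0)/T(t), and the result exceeds the measured total whenever f(t) > T(t)/T(0). That cannot hold when P_obs = P_Alive + P_Dead. On the assumed grid, T(0)/T(t) is about 2 to 16 at 24 h and 12 to 680 at 48 h.
- If f(t) is relative to the dosing-time sample, the SAP's rule is correct and the overstatement is nil.

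**3. Trace of the ex vivo endpoint**

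It is present in the protocol synopsis and section 3, and its objective is in SAP 3.4.2. It is absent from protocol 9.4.3, SAP 3.5.2, SAP section 11 and Table A. None of these absences depends on SAP 10.5.2, so restoring viable counts to the PD dataset would not supply the missing analysis.

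**The case against.** The strongest reply is that 10.5.2 is loosely worded and does not amount to a decision to discard data. It names only concentrations for removal, its parent dataset holds viable counts, and 10.6.3 and 10.7 both expect them. Its content list joins two items with a comma and no conjunction, so an item may have been dropped. This stands as far as intent goes: the sections conflict. But the list is explicit, SAP 10.2 does not name viability among the data sources, and 10.5.2 gives censoring and transformation rules for total counts with none specific to viable counts. An analyst following it would have no viability data to fit.

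A reader might infer that the derived parameters would then carry no trial information on killing. That is too strong. The fallback concerns one model of three. EC50 and Hill are still estimated from the trial or, for Hill, chosen by BIC. MPC90 = EC50 × 9^(1/Hill) contains no Emax term. Total counts narrow the answer to two discrete solutions at saturating concentration, and falling concentrations or regrowth may add information.

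A reader might also infer that the scaling is simply wrong. Protocol 8.2.2 reads most naturally as a per-sample fraction, but it gives no denominator, and a pre-dose culture is taken, so a fraction relative to dosing is possible.

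Finally, protocol section 9 foresees a separate Modelling Analysis Plan, which is not one of the two documents and may hold more. Protocol 9.4.2, however, places full modelling detail in the SAP. Protocol 8.2.2 also describes ex vivo results as supportive of the clearance endpoint, and life-stage qRT-PCR outputs may serve the objective's molecular part. Neither gives ex vivo growth an analysis in the SAP.

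**Conclusion.** Three separate defects stand.

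1. SAP 10.5.2 conflicts with 10.5 and 10.6.3. Applied literally, it fixes Emax in the Clearance model at an unstated in vitro value despite the viability samples collected. The ambiguity this leaves is 5.25 against 2.08 in log10 PRR48 in the worked example, and 1.0 to 3.3 apart over the assumed grid. These sizes rest on assumed rates, known GR and saturating concentration; the exchange of the two rates follows from the SAP's equations under the last two conditions.
2. The denominator of the viable fraction is undefined. The error is nil under one definition and equals the fold-fall in total parasitaemia under the other.
3. The ex vivo secondary endpoint has no analysis in either document and no declared removal.

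It would be tempting to say that the endpoint is lost because of 10.5.2. The documents do not support that link: the two gaps are independent and need separate fixes. The point matters for the primary endpoint only if the Clearance model is selected or relied on.

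**What to change.** - **SAP 10.5.2:** keep viable counts as a second observation type with their own error model and censoring rule. Fit P_Alive to viable counts jointly with P_obs to total counts.
- **SAP 10.6.3:** if Emax must still be fixed, state the in vitro value, its source and a sensitivity range.
- **SAP 10.5:** define the denominator of the viable fraction. If it is the current sample, multiply by the total count at the same time. If it is the pre-dose sample, say so and keep the present rule.
- **SAP 3.5.2, section 11 and Table A:** add an ex vivo viability analysis by dose group, with a method and non-detect rule specified for that assay, and a listing and table. Otherwise declare its removal in SAP 13. In either case bring protocol section 3 and protocol 9.4.3 into agreement on the number of secondary endpoints.

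The cost is wording, one dataset rule, one added observation type in the model and one secondary analysis. The scheduled samples suffice.
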